3.4 Primary Safety Endpoints

- Incidence of all serious adverse events including unanticipated adverse effects (balloon migration, small bowel obstruction, luminal GI perforation, ulcer formation, liver abscess formation, bleeding, biliary obstruction or injury, aspiration, infection, abdominal pain requiring hospitalization, nausea and dehydration requiring intravenous fluids, and death). All adverse events will be captured and graded for severity using standardized scales. [24]
- Early balloon intolerance requiring removal.
- Balloon deflation rates (see Orbera PMA)

4 Subject Selection, Enrollment and Withdrawal

We plan to enroll patients with obesity and NASH with fibrosis but no advanced fibrosis or cirrhosis as diagnosed by MRE/MRS . We are expanding the cohort of patient with obesity to include patients with BMI between 30 to 55 kg/m² given recent meta-analysis demonstrating similar weight loss with the Orbera intragastric balloon in obese patients with higher BMIs (Figure 3).[6] Given that more than 10% TBWL is associated with improvement in NASH [5], we feel that including patients with higher BMI will be important in this pilot study.

[figure not shown]

Figure 3. Meta-regression linear plot depicting the best-fit regression line of the association between baseline body mass indexes (BMIs) and percentage of excess weight loss (%EWL) at 6 months after Orbera intragastric balloon (IGB) implantation. The sample size of individual studies is proportional to the diameter of the circle by which it is represented on the graph. [6]

4.1 Inclusion Criteria

- Age 21 – 70 years
- Male and Female
- BMI between 30 to 55 kg/m²
- NASH with fibrosis (excluding advanced fibrosis or cirrhosis). This is determined by a baseline liver biopsy when available showing stage 1-3 fibrosis, but *not* stage 4 (advance fibrosis or cirrhosis), and / or magnetic resonance elastography (MRE) showing a liver stiffness measurement range that spans a score of ≥ 3.0 kPa and with a mean liver stiffness value of < 5 kPa. Both of these tests are valid for study inclusion within 6 months of enrollment. When both a biopsy and MRE are available prior to study enrollment the fibrosis designation will be based on the gold standard histology.
- Subjects will have attempted and failed more conservative weight reduction alternatives, such as supervised diet, exercise and behavior modification programs (per Orbera’s approved PMA: P140008)
- Able to provide a written informed consent

4.2 Exclusion Criteria

- Age < 21 or > 70 years
- Pregnancy or plan for pregnancy during study period
- Lactation
- Previous history of gastric surgery

- Hiatus hernia > 5cm
- Current or recent (within 6 months) gastric or duodenal ulcers
- Gastroparesis
- Liver cirrhosis
- Coagulopathy or active use of anticoagulation
- Inflammatory bowel disease involving the upper GI tract.
- Active substance abuse
- Active psychiatric condition deemed as a contraindication by our psychology team evaluation
- Concomitant chronic liver disease other than NASH
- Potential upper gastrointestinal bleeding conditions such as esophageal or gastric varices, congenital or acquired intestinal telangiectasis, or other congenital anomalies of the gastrointestinal tract such as atresias or stenosis
- Hiatal hernia with associated severe or intractable gastro-esophageal reflux symptoms
- Structural abnormality in the esophagus or pharynx such as a stricture or diverticulum that could impede passage of the delivery catheter and/or an endoscope
- Achalasia
- Gastric mass
- Patients receiving aspirin, anti-inflammatory agents, anticoagulants or other gastric irritants, not under medical supervision
- Patients who are unable or unwilling to take prescribed proton pump inhibitor medication for the duration of the device implant.

4.3 Subject Recruitment, Enrollment and Screening

Patients with suspicion for NASH at our center undergo MRE (magnetic resonance elastography) sequence to classify their disease as grade 0 (simple steatosis), grade 1 (steatohepatitis with no fibrosis), grade 2 (steatohepatitis with early fibrosis), grade 3 (steatohepatitis with advance fibrosis/cirrhosis). Those with stage 1-3 fibrosis and interested in weight loss with the intragastric balloon will be referred for the intragastric balloon clinic evaluation, which consist of one day evaluation by nutrition, psychology, and gastroenterology in the obesity clinic. Those who meet the inclusion / exclusion criteria will be consented to participate in the study after discussion of risk, benefits, and alternatives by one of our study team members and a written consent is provided. Those who do not qualify for the study will be offered other alternatives for weight loss as per out clinical protocol. Of note the cost of balloon placement, removal, medications to manage symptoms after balloon placement, EUS guided liver biopsy and pathologic interpretation, and the 12 months life-style intervention program will be covered by the study. The initial evaluation at the obesity clinic prior to enrollment in the study will be part regular clinical care.

4.4 Early Withdrawal of Subjects

4.4.1 When and How to Withdraw Subjects

Study will be stopped:

- 1 death

- 2 or more severe adverse events or unanticipated adverse device effects deemed of enough severity to stop the study by an independent data safety and monitoring board consisting of three Mayo consultants independent from the study

Patient will be withdrawn from the study:

- Subject safety issues, adverse device effects
- Failure of subject to adhere to protocol requirements
- Disease progression to cirrhosis within the time frame of the study
- Subject decision to withdraw from the study (withdrawal of consent)

Replacement of withdrawn subjects:

If a patient is withdrawn from the study for reasons other than severe adverse events, the intragastric balloon will be removed from the patient at a time that works for the patient and within six months of insertion. The patient will be followed as per the standard clinical protocol for the intragastric balloon to ensure safety. Weight and safety data will be collected until the intragastric balloon is removed. After balloon removal subjected will be followed clinically as per our protocol for additional three months to ensure safety. We will replace up to 5 subjects withdrawn for reasons other than severe adverse events.

4.4.2 Data Collection and Follow-up for Withdrawn Subjects

If a patient is withdrawn from the study for reasons other than severe adverse events, the intragastric balloon will be removed from the patient at a time that works for the patient and within six months of insertion. The patient will be followed as per the standard clinical protocol for the intragastric balloon to ensure safety. Weight and safety data will be collected until the intragastric balloon is removed. After balloon removal subjected will be followed clinically as per our protocol for additional three months to ensure safety. We will replace up to 5 subjects withdrawn for reason other than severe adverse events.

5 Study Device

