3.3 Secondary Study Endpoints

- Regression of fibrosis on paired EUS guided liver core biopsies.

- Percent total body weight loss at 6 months after Orbera balloon placement.
- Obtaining lipid saturation (SI) and polyunsaturation (PUI) indices via H-MRS technology pre- and post-intervention
- Obtaining hepatic triglycerides content (HTGC) via H-MRS technology pre- and post-intervention.
- Obtaining percent unsaturated fatty acyl chains present in this cohort of NASH patients, as well as changes that occur in the setting of weight loss.
- Obtaining percent polyunsaturated fatty acyl chains present in this cohort of NASH patients, as well as changes that occur in the setting of weight loss.
- Measurement of hepatic lipid composition by needle biopsy and lipidomic analysis techniques before and after weight loss.
- Correlation of MRS obtained lipid composition to lipidomic analysis composition

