6.3 Tissue lipidomics workup

A total of 50 mg of liver tissue will be collected via EUS-guided biopsy. Sharkcore needle is 22 gauge. Diameter is ~0.7 mm. ~270 mm of tissue length will be acquired and will deliver a volume of ~50 mg. The sample will be frozen in liquid nitrogen immediately upon harvesting in the endoscopy suite and placed in a 1.5 conical Eppendorf tube. Samples shall not sit more than few minutes before flash freezing to ensure adequate analysis. Also, inspection before freezing will occur to ensure that the tissue is relatively clean specimen on inspection.

7 Statistical Plan

Baseline subject characteristics will be described by their means, medians and and/or frequencies. For our primary study endpoint of improvement in NASH activity scores on paired liver biopsies at baseline and after 6 months, we will be using a paired t-test with two sided alpha <0.05. With a sample size of 20 subjects, we will have 80% power to detect a medium to large difference in activity scores (0.66). Please see table below for minimum sample size needed for each desired effect size.

	Small effect size 0.5	Medium effect size 0.66	Large effect size 0.8
Sample (N)	34	20	15

Additionally, we will run a linear regression analysis with the change in NASH activity scores as the outcome with baseline BMI and diabetes as the covariates on a univariable and multivariable fashion to investigate their effects on the primary outcome.

For our secondary endpoint of number of subjects with regression of fibrosis in paired liver biopsies, we will be reporting the percentage of subjects with regression. As far as the secondary endpoint of percent total body weight 6 months after Orbera balloon placement, we will be reporting the mean or median percent total body weight loss at 6 months.

For our secondary endpoint of quantifying total fat liver and triglycerides content, we will be reporting the mean and median percent of change at 6 months.

8 Safety and Adverse Events

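### Withdrawn subjects whose balloon is removed early have no specified Month 6 weight and the weight analysis set is undefined, so the reported 6-month weight loss may be biased, probably upward

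*Combined protocol and SAP*

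**What the plan says.** - **Endpoint.** Section 3.3 lists "Percent total body weight loss at 6 months after Orbera balloon placement" as a secondary endpoint. The clock runs from placement, not from removal.
- **Weight after withdrawal.** Sections 4.4.1 and 4.4.2 carry essentially the same paragraph. It opens "If a patient is withdrawn from the study for reasons other than severe adverse events, the intragastric balloon will be removed from the patient", with the timing given as "at a time that works for the patient and within six months of insertion". It continues: "Weight and safety data will be collected until the intragastric balloon is removed".
- **Follow-up after removal.** "After balloon removal subjected will be followed clinically as per our protocol for additional three months to ensure safety". No weight measurement is named for this period.
- **Severe adverse events.** The paragraph is limited by its opening condition. Neither section gives a data-collection rule for subjects withdrawn because of a severe adverse event.
- **Replacement.** "We will replace up to 5 subjects withdrawn for reason other than severe adverse events".
- **General schedule.** Sections 3.1, 5.4 and 6 take weight at baseline, at balloon removal (labelled as 6 months) and at 12 months. They treat removal and Month 6 as the same date. Yet Section 3.4 makes early intolerance leading to removal a safety endpoint.
- **Analysis.** Section 7 says "we will be reporting the mean or median percent total body weight loss at 6 months". It defines no analysis set and no handling of missing weights. The instruction in Section 8.10 to explain missing data concerns completion of the case report form, not analysis.

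**The concern.** A fixed-time endpoint needs a measurement at that time in everyone it is meant to describe. Under the stated rule, a subject withdrawn with the balloon out at Month 2, say, gives a weight at Month 2 and none is required later. The withdrawal reasons in Section 4.4.1 include adverse device effects and non-adherence. Both plausibly go with shorter device exposure and less weight loss, so the missing weights are unlikely to be a random subset. Replacing such subjects with others who stay in the study could add to the selection.

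Weight loss is the mechanism in Hypothesis 1, and the rationale in Sections 1.5.1 and 2.1 rests on the balloon producing about 13% loss, above the 10% level tied to histological benefit. A mean weighted towards those who kept the balloon describes people who tolerate it, not people in whom one is placed. Unlike the second biopsy, a weight needs no procedure, so most of this loss of data is avoidable. A Month 6 weight that is missed cannot be recovered later.

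**Working it through.** **Plan's own figures.** No sample size or precision is stated for the weight endpoint. The only calculation is for NAS: a paired t-test, two-sided 0.05, effect size 0.66, n = 20. The exact noncentral-t power there is 79.9%, so the stated 80% reproduces. The enrolment of 25 is 20 + 5, which equals 20/(1 − 0.20). Neither figure depends on the weight rule.

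**Following one subject through the text.** A balloon is placed, the subject is withdrawn for a reason other than a severe adverse event, and the balloon comes out before Month 6.
1. Section 4.4.2 ends weight collection at removal.
2. The three further months are clinical safety follow-up with no weight named. They would reach Month 6 only if removal was at Month 3 or later.
3. Section 7 does not say whether this subject is excluded, counted as missing, or given the weight at removal as the Month 6 value.

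For a withdrawal due to a severe adverse event, step 1 has no rule at all.

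**Size.** Inputs:
- Mean loss in subjects with a Month 6 weight: 13.16%, the pooled 6-month figure in Section 1.1, taken as an assumption.
- N, subjects implanted: 25, the planned maximum.
- w, subjects with no Month 6 weight: not given. I use 5 (the whole replacement allowance) and 2. Neither is an expected rate.
- m, mean loss at Month 6 in those subjects: not given. I use 0 to 13.16%, including the pooled 12-month (11.27%) and 3-month (12.3%) figures from the same sentence. Those two are not data on early removal.

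Mean over all implanted = [(N − w) × 13.16 + w × m]/N

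Overstatement = (w/N) × (13.16 − m)

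Example, w = 5 and m = 0: (20 × 13.16 + 5 × 0)/25 = 10.53, and 13.16 − 10.53 = 2.63.

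| m (%) | Mean, 5 of 25 missing | Overstatement | Mean, 2 of 25 missing | Overstatement |
|---|---|---|---|---|
| 0 | 10.53 | 2.63 | 12.11 | 1.05 |
| 5 | 11.53 | 1.63 | 12.51 | 0.65 |
| 8 | 12.13 | 1.03 | 12.75 | 0.41 |
| 11.27 | 12.78 | 0.38 | 13.01 | 0.15 |
| 12.3 | 12.99 | 0.17 | 13.09 | 0.07 |
| 13.16 | 13.16 | 0 | 13.16 | 0 |

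A smaller denominator gives a larger effect. With N = 20 and m = 0, 2 missing gives (2/20) × 13.16 = 1.32 points, and 5 missing gives (5/20) × 13.16 = 3.29. The sign follows m: the difference is positive when m is below 13.16 and negative when m is above it. The formula applies to the mean; Section 7 leaves the choice between mean and median open.

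**The case against.** A reader might infer that a 6-month weight exists only for subjects who kept the balloon, and that the reported figure is therefore overstated. The documents do not support either step in that form.

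- **Not only those who kept the balloon.** Section 4.4.1 does not make early removal for intolerance an automatic withdrawal. A subject who is not withdrawn arguably stays on the general schedule, with weights at 6 and 12 months, although tying the 6-month weight to removal leaves this unclear. A withdrawn subject may also keep the balloon for up to six months and be weighed until it comes out. One can argue too that the general schedule still covers withdrawals due to severe adverse events, since nothing expressly switches it off.
- **Not a stated completer analysis.** Section 7 neither excludes withdrawn or replaced subjects nor rules out using the weight at removal. The analysis set is undefined.
- **Bias not shown.** Neither the number withdrawn nor their weight loss is in the documents. Some withdrawals eligible for replacement (progression to cirrhosis, withdrawn consent) need not reflect poor tolerance, and withdrawals for severe adverse events are not replaced.
- **No like-for-like claim.** The documents do not say whether the pooled 13.16% comes from completers or from all implanted subjects, and Section 7 plans no test against it or against 10%. It cannot be said that a completer mean would flatter the device in that comparison.
- **Low rank.** This is a descriptive secondary endpoint in a small single-arm pilot.

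All of these limit the claim, and all are accepted. They do not remove the stated rule. For withdrawals other than those due to severe adverse events, the text itself ends weight collection at removal, and no provision elsewhere specifies how the 6-month endpoint is then obtained.

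**Conclusion.** The point holds as a gap in data collection and analysis definition. Withdrawn subjects with early removal have no specified Month 6 weight, withdrawals for severe adverse events have no weight rule in the section meant to supply one, and Section 7 does not say who enters the mean. That mean may be biased. The direction is probably upward, because adverse device effects and non-adherence plausibly go with less weight loss, but this is a judgement and not a finding from the documents.

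If observed subjects average 13.16% and N is 25, the overstatement runs from about 0 to 2.6 points with 5 weights missing and from about 0 to 1.1 points with 2 missing. The upper ends require that those subjects lose nothing by Month 6. The bias is zero if they lose as much as the others. The primary NAS analysis and its sample size are unaffected. The change is worth making because the weights are easy to obtain at the time.

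**What to change.** **Sections 4.4.1 and 4.4.2.** Replace the sentence that ends weight collection at removal with: *Weight will be measured at Month 6 and Month 12 after placement in every subject in whom a balloon was placed, whatever the date of or reason for removal or withdrawal, including severe adverse events, unless consent is withdrawn.*

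**Section 7.** Add:
- percent total body weight loss at 6 months after placement is reported over all implanted subjects, including those later replaced, with the completer figure beside it;
- the number with no Month 6 weight is reported with reasons;
- a simple sensitivity analysis covers weights still missing, for example setting the loss to 0% and, separately, using the last recorded weight.

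**Consistency.** The schedule in Section 6.2 attaches weight only to the screening examination, while the text of Section 6 has weights at 6 and 12 months. This is a separate inconsistency, but the same edit can reconcile it.

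**Cost.** Up to two extra weights for a handful of subjects, and possibly a slightly less favourable headline figure. Weights lost through withdrawn consent will not be recovered, which is why the sensitivity analysis is needed. No change to the timing of removal or to clinical care is proposed.

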8.2 Adverse Event Reporting Period

For this study, the study treatment follow-up period is defined from enrollment in the study to 6 months after balloon removal (12 months from balloon insertion). Adverse events will be captured and reported from enrollment to the end of the study treatment follow-up.

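### For subjects withdrawn without a severe adverse event, Section 4.4 ends safety data at balloon removal, 6 months before the adverse event window in Section 8.2 closes

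*Combined protocol and SAP*

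**What the plan says.** Section 4.4.1 lists four reasons for withdrawing a patient. The first is "Subject safety issues, adverse device effects"; the others are non-adherence, progression to cirrhosis and the subject's own decision. Sections 4.4.1 and 4.4.2 then give the same rule for most of these subjects. It opens "If a patient is withdrawn from the study for reasons other than severe adverse events", requires removal of the balloon within six months of insertion, and continues: "Weight and safety data will be collected until the intragastric balloon is removed". The next sentence is "After balloon removal subjected will be followed clinically as per our protocol for additional three months to ensure safety". Section 4.4.2 ends: "We will replace up to 5 subjects withdrawn for reason other than severe adverse events".

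Section 8.2 sets the adverse event window for the study. It says that "the study treatment follow-up period is defined from enrollment in the study to 6 months after balloon removal (12 months from balloon insertion"), and then: "Adverse events will be captured and reported from enrollment to the end of the study treatment follow-up". It neither mentions withdrawn subjects nor refers to Section 4.4.

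The first primary safety endpoint in Section 3.4 is "Incidence of all serious adverse events including unanticipated adverse effects". The other two are early intolerance leading to removal, and balloon deflation.

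**The concern.** Two rules cover the same data in the same subjects and stop at different times. Section 4.4 closes the safety record at removal. Three months of clinical follow-up come next, but no text says that new events found then become study data. Section 8.2 keeps the record open for 6 months after removal.

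If 4.4 is followed as written, a subject withdrawn because of a non-severe device effect has a shorter safety record than one who completes the study. The subjects who tolerate the balloon poorly are then observed for less time. A serious adverse event that first appears some weeks after removal in such a subject might not enter the count for the first safety endpoint.

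**Working it through.** The plan gives no figure on this point to reproduce, and the sample-size figures in Section 7 play no part in it. The check sets the end dates side by side and then sizes the difference.

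**End dates.** Let removal be at month *t* after insertion. Section 4.4.2 ends safety data at *t*; its clinical follow-up ends at *t* + 3; Section 8.2 ends adverse event capture at *t* + 6.

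| Removal at month | Safety data end (4.4.2) | Clinical follow-up ends (4.4.2) | Adverse event capture ends (8.2) |
|---|---|---|---|
| 1 | 1 | 4 | 7 |
| 2 | 2 | 5 | 8 |
| 3 | 3 | 6 | 9 |
| 6 | 6 | 9 | 12 |

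The difference is 6 months whatever the removal date, or 3 months if events from the clinical follow-up are recorded.

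**What other sections recover after removal.**
- Sections 5.4 and 6: the principal investigator evaluates all patients within 1 week of removal. Section 8.3 has adverse events solicited at each visit or contact, so early events should be found.
- Section 6.1: device-related events or gastric ulcers present at removal are followed until they resolve.
- Section 8.1, post-study events: unresolved events are followed, and deaths or events plausibly related to the study are to be notified at any time after discontinuation. This route is passive and needs a judgement of relatedness.

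None of these sets a period of active collection for new events in withdrawn subjects. The remaining gap is new events that arise after the one-week evaluation and that nobody links to the study.

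**Size.** The Study Summary gives 25 subjects: 20, plus 5 in case of early withdrawal. The number who will withdraw is unknown. Assume *k* = 1 or 5 withdrawn, removal at Month 1, and 12 months for everyone else.

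Subject-months = (25 − *k*) × 12 + *k* × (end month).

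- *k* = 1: 24 × 12 = 288. Under 4.4.2: 288 + 1 = 289. With clinical follow-up recorded: 288 + 4 = 292. Under 8.2: 288 + 7 = 295. Loss under 4.4.2: 6/295 = 2.0%.
- *k* = 5: 20 × 12 = 240. Under 4.4.2: 240 + 5 = 245. With clinical follow-up recorded: 240 + 20 = 260. Under 8.2: 240 + 35 = 275. Loss under 4.4.2: 30/275 = 10.9%.

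The removal month matters little. With *k* = 5 and removal at Month 6, the loss is 30/300 = 10.0%.

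**One event.** With all 25 subjects as the denominator (an assumption, since Section 3.4 names none), 1 event is 1/25 = 4.0%, exact 95% interval 0.1% to 20.4%. Two events are 2/25 = 8.0%, interval 1.0% to 26.0%. One missed event therefore moves the reported incidence by 4 percentage points.

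**The case against.** The strongest reply is that 4.4.2 is the specific rule for withdrawn subjects and displaces the general rule in 8.2. A shorter window after withdrawal is a common choice, and one of the four withdrawal reasons is withdrawal of consent. This reading is available, but 8.2 does not state it. The other three reasons do not in themselves prevent contact. If the shorter window is intended, it shortens observation for subjects withdrawn because of device effects, and the plan should say so.

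The second reply is that existing safeguards leave little to lose. This largely stands and limits the point to new, later events.

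The third is that the size is modest: no person-time analysis is planned, so the subject-months feed no stated result, and the intervals above overlap widely and would be no narrower after the change. This also stands.

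A reader might infer more than the documents support:
- **Two end dates inside 8.2.** Taken literally, 6 months after removal and 12 months from insertion differ when removal is early. The bracket is better read as a gloss on the planned schedule. Sections 3.1, 5.4 and 6 pair the same two times for the Month 12 measurements. It merits a clarification but is not a second rule.
- **A larger loss, measured against 12 months for everyone.** That comparison treats the gloss as a rule. The operative definition in 8.2 is 6 months after removal, so the comparators are 295 and 275.
- **An effect on the stopping rule.** Section 8.6 does not act on a bare count of two: apart from a death, events must be judged severe enough to stop the study. Deaths and plausibly related events are notifiable under 8.1, and subjects withdrawn for severe adverse events fall outside the 4.4 sentence.

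**Conclusion.** The inconsistency is real and of low priority. For subjects withdrawn without a severe adverse event, safety data end at removal under 4.4 and 6 months later under 8.2. The one-week evaluation, the follow-up of events present at removal and the post-study rule cover much of the difference. New, later events remain exposed, and losing them could under-count the serious adverse event endpoint.

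The loss of follow-up is 2.0% with one withdrawal and 10.9% with five, assuming 25 subjects and removal at Month 1. Five is the number the protocol is prepared to replace, not a forecast or a cap. The documents give no rate for events after removal, so the number of events missed cannot be estimated; it is probably small.

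Efficacy is not affected. Early intolerance is known at removal and deflation occurs while the balloon is in place, so neither endpoint can be lost through a cutoff at removal.

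**What to change.** In 4.4.1 and 4.4.2, replace the sentence on weight and safety data with: *Weight is collected until balloon removal; adverse events are solicited and recorded until 6 months after removal, as in 8.2, unless the subject withdraws consent to contact.* Use the three months of clinical follow-up already planned and the monthly bariatric clinic phone calls in the Section 6.2 schedule.

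In 8.2, clarify that the 12-month equivalent applies when removal is at Month 6. In the report, give each withdrawn subject's removal date and months of follow-up after it.

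The cost is a sentence in each part of 4.4, a few words in 8.2 and up to 6 phone calls per withdrawn subject. No visit or procedure is added. Some withdrawn subjects will refuse contact, and their follow-up will still end early.
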